Chronic treatment with reserpine produces a different spectrum of effects than brief (single or only a few doses) treatment with reserpine. In contrast to the reversal of reserpine-induced hypolocomotion by d-amphetamine, rats chronically treated with reserpine are more sensitive to the acute stimulant effects of d-amphetamine. Although chronic reserpine-treated mice show an increased sensitivity to the toxic effects of amphetamine, no increase in lethality was seen (Stolk and Rech 1968). Chronic reserpine and amphetamine seem to produce similar effects with decreased self-stimulation responding in animal models (Leith and Barrett 1980).

Explicit mortality data was not presented in any of the studies described above. However, there were no comments suggesting an increased mortality in animals treated with reserpine and amphetamine (or cocaine).

4. Methods

a. Study Design

This 7-day double-blind, parallel-group, placebo-controlled inpatient study will compare the effects of 15 mg of intravenous methamphetamine given 60 hours before and 12 hours after a single oral dose of reserpine (0.5 or 1.0 mg) or placebo.

Subjects will be randomized to one of three parallel groups. A parallel group design (as opposed to a crossover design) is needed because the duration of action of even a single dose of reserpine is unpredictable. Reserpine irreversibly binds to the vesicular monoamine transporter; reversal of this effect requires synthesis of new transporter, a process that can take from one week to one month.

b. Methods of Data Analysis

As appropriate, statistical group comparisons will be made with PC-SAS's general linear model procedure (SAS Institute Inc., Release 6.04 Edition, Cary, NC, 1990) and with multifactor repeated-measures analysis of variance using SAS (UNIX) or SuperANOVA (Macintosh) software applications. Physiologic data will be transformed to change scores (post-treatment minus pre) and analyzed by repeated measures analysis of variance (ANOVA). After a significant F test, pairwise comparisons will be performed using the least squares means analysis. Effects will be considered statistically significant at P = 0.05.

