Subjects will be recruited through advertisements placed on Craig's list (a community Internet site) and advertisements in Bay Area newspapers.

e. Consent Process and Documentation

Informed consent will be obtained prior to study procedures in all subjects.

f. Procedures

1) Study Procedures

Screening. During their first visit to the laboratory, subjects will complete routine screening questionnaires, undergo a 12-lead EKG, and provide blood and urine samples for screening chemistries. Their second visit will involve a detailed history and physical exam by a physician (JM, or DH).

Drug Doses and Conditions

Reserpine Dosing. Subjects will be admitted to the GCRC for the entire study duration and at least 1 day before the first methamphetamine challenge. Reserpine (or placebo in the placebo group) will be administered at approximately 10 PM on the 4th hospital day. After successful screening, subjects will be randomly assigned to one of 3 parallel groups each containing 10 subjects. All groups receive methamphetamine 15 mg 60 hours before and 12 hours after reserpine. Groups are:

- 1. Reserpine 0.5 mg
- 2. Reserpine 1.0 mg
- 3. Placebo for reserpine

Methamphetamine Dosing. Methamphetamine 15 mg will be given on day 2 (60 hours before) and 12 hours after reserpine or placebo on day 4. Methamphetamine will be administered over 1 minute under infusion pump control.

Subjects will not be dosed if they have a positive qualitative urine test for abused drugs on the morning of dosing. Caffeine-containing beverages will not be allowed for 12 hours before each methamphetamine dose. No smoking will be allowed at any time after GCRC admission; nicotine patches will be offered to all smokers but discontinued 12 hours prior to methamphetamine doses. Although subjects will be in mild nicotine withdrawal at the time of methamphetamine dosing, avoiding drug-drug interactions between nicotine and methamphetamine or reserpine should decrease variability and improve our ability to detect subtle interactions between methamphetamine and reserpine.

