Physiological Monitoring. On the days without methamphetamine challenges (days 0, 2, 3, and 5), subjects will have vital signs (heart rate, standing and supine blood pressure, respiratory rate, oxygen saturation, core temperature, and weight) and the noninvasive cardiac profile determined daily at 10 AM, 4 PM, and 8 PM. Vital signs will be obtained using a Critikon or Escort II monitor or a similar bedside device and noninvasive cardiovascular parameters measured using the instruments described above. On the days methamphetamine challenges are performed (study days 1 and 4), vital signs and the noninvasive cardiac profile will be obtained 15 minutes before and 5, 15, 30 and 60 minutes and at 1, 2, 3, 4, 6, 8 12, 18, 24, 30 36 and 48 hours after the infusion.

Subjective Measures. Subjective measures will be obtained daily at 8 AM, 4 PM, and 8 PM on study days 0, 2, 3 and 5. On days 1 and 4, when methamphetamine is administered, measures will be obtained starting 15 minutes before, and at 5, 15, 30, and 60 minutes, and 1, 2, 3, 4, 6, 8 12, 18, 24, 30 36, and 48 hours after the infusion. Items will include "any drug effect," "good drug effect," "bad drug effect," "headache," "dizziness," "desire for methamphetamine," and "craving for methamphetamine." The Beck Depression Inventory (Beck et al. 1996) will be administered daily at 4 PM.

Biosample Measures. All urine will be collected in 24-hour intervals and assayed for MHPG-sulfate by HPLC. On days 1, 4, and 6, aliquots will be sent for qualitative drugs of abuse screens.

Cardiovascular Measures. A series of non-invasive complementary cardiovascular measures assessing ventricular function (impedance cardiography), cardiac conductance and repolarization (ECG QTC interval), and peripheral vascular dynamics (impedance cardiography) will be obtained frequently throughout hospitalization. Data acquisition for the entire non-invasive panel requires about 10 minutes.

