If any of the following occur during or within 2 hours of methamphetamine dosing in the first challenge session, the subject will not continue in the study:

- 1. Supine heart rate > 80% predicted maximal for age or <50, systolic blood pressure >210 or <90, diastolic blood pressure >120 or <50, respiratory rate >24 or <8.
- 2. Significant arrhythmia defined as ≥6 beats nonsinus supraventricular tachycardia or =3 beats ventricular tachycardia.
- 3. Reported chest pain or dyspnea.
- 4. Subject confusion, agitation or inability to properly complete test procedures.
- 5. Any other adverse effect regarded as being due to methamphetamine or the experimental procedures.

If unexpected abnormal vital signs occur, subjects will be closely observed with vital sign measurements every 5 minutes until the abnormalities abate. If stopping criteria are exceeded, subjects will be closely observed for at least 24 hours before being discharged from the GCRC.

Alterations in CNS norepinephrine turnover produced by methamphetamine and reserpine will be assessed using urinary MHPG-sulfate excretion. Methamphetamine pharmacokinetic profiles will not be obtained because it is unlikely that alterations in the biodisposition of methamphetamine will be related to any pharmacodynamic effects. Reserpine pharmacokinetic profiles will not be obtained because venous levels are unrelated to pharmacologic effects. Subjective pharmacodynamic effects will be assessed with symptom reports and measured with visual analog scales.

Biological Samples

Urine Samples. All urine will be collected in 24-hour intervals (starting at 9:30 AM daily) and analyzed for MHPG-sulfate. A drug of abuse screen will be performed on admission and every 48 hours while on the GCRC and just before each methamphetamine dose.

2) Time (Frequency and duration of each study procedure; total amount of time)

Screening. The first visit to the laboratory will last 1 to 2 hours; subjects will complete routine screening questionnaires, undergo a 12-lead EKG, and provide blood and urine samples for routine labs. If subjects are called for a second visit, they will be compensated (see k below); this visit will involve a detailed history and physical exam by a physician and stress echocardiography, and will last approximately 2 to 3 hours.

Study Sessions. Subjects will be admitted to the UCSF General Clinical Research Center (GCRC) at Moffitt Hospital 24 hours before the first methamphetamine challenge. They will remain on

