the ward until 48 hours after the last methamphetamine challenge dose. The total duration of GCRC admission is 5 nights.

3) Study Sites

Study procedures will be carried out at the UCSF General Clinical Research Center.

g. Risks/Discomforts

The most common side effects with intravenous methamphetamine are palpitations, euphoria, anxiety, panic, or dyspnea. In multiple prior experiments where similar or larger doses of intravenous methamphetamine have been administered (up to 0.5 mg/kg), few adverse effects have been seen or reported. Based on our prior experience, we expect the effects of the proposed 30-mg dose to be mild in intensity and brief in duration.

We will administer a single oral 0.5 or 1.0 mg dose of reserpine. This dose is safe, has pharmacologic activity, and is generally well tolerated. Adverse reactions are dose related and usually mild, with the majority affecting the CNS. Sedation and inability to concentrate are commonly reported. With *repeated* doses *greater* than 1.0 mg/day, depression and suicide can occur. Although serious depression with daily doses less than 1.0 mg per day has been reported, a history of depression is often present. Depression usually occurs insidiously, over a period of weeks or months and resolves with discontinuation of the drug; there are no reports of depression or suicide following a single dose of reserpine. Other reported side effects include nasal congestion and dyspepsia (Hardman et al. 1996).

There is a moderate amount of pain, discomfort, bruising, and a very remote potential for infection associated with the placement of needles in arm veins for drug administration.

There is also likely to be some stress from the fact the subject will be living on a hospital ward, and will be subjected to repeated blood sampling, physiological monitoring, questionnaires, and other study procedures. We will make every effort to minimize such stress.

h. Treatment and Compensation for Injury

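### The protocol states a 5-night stay, but its own timetable takes 144 h (6 nights), and the $858 payment maximum carries the same miscount

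*Protocol*

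**What the plan says.** Section 4.f.2 (Time, Study Sessions) fixes the start of the stay: "Subjects will be admitted to the UCSF General Clinical Research Center (GCRC) at Moffitt Hospital 24 hours before the first methamphetamine challenge". Section 4.f.1 (Reserpine Dosing) makes that lead time a minimum: "at least 1 day before the first methamphetamine challenge". The same paragraph sets the dosing intervals: "All groups receive methamphetamine 15 mg 60 hours before and 12 hours after reserpine", with reserpine at about 10 PM on the fourth hospital day. Section 4.f.2 then sets the end of the stay and gives a total; subjects stay on "the ward until 48 hours after the last methamphetamine challenge dose. The total duration of GCRC admission is 5 nights".

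Other statements bear on the length of stay:

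- Section 4.a describes "This 7-day double-blind, parallel-group, placebo-controlled inpatient study".
- Section 4.f.1 (Physiological Monitoring) ends the post-infusion schedule at "18, 24, 30 36 and 48 hours after the infusion".
- Section 4.f.1 (Biosample Measures) adds: "On days 1, 4, and 6, aliquots will be sent for qualitative drugs of abuse screens".
- Section 4.f.1 (Subjective Measures) says the Beck Depression Inventory "will be administered daily at 4 PM".
- Section 4.f.1 (Urine Samples) runs 24 h collections from 9:30 AM.
- Section 4.k pays $30 for the second screening visit, $150 per night on the ward and a 10% bonus for completing everything, and gives the maximum as $858.

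**The concern.** The total number of nights follows directly after the rule that determines it and does not agree with that rule. These are operative figures: one is the length of stay a ward would book, the other the most a volunteer can expect to be paid. Because section 4.k pays by the night, a completer on the stated timetable earns more than the stated maximum, so the rate and the maximum also conflict.

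What is at stake depends on which sentence is followed. Under the 48 h rule no data are lost and only the stated stay and maximum payment are wrong. Under the 5-night figure the end of the stay is cut, and with it some data for two hypotheses in section 2: urinary MHPG-sulfate (item d) and Beck scores on the days after methamphetamine (item f). Observation after the drug combination, the exposure the study exists to examine, would also be shorter. Cutting the front of the stay instead would break the 24 h admission rule.

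**Working it through.** **Length of stay.** The inputs are the four intervals in sections 4.a, 4.f.1 and 4.f.2. Reserpine at 10 PM puts both infusions at about 10 AM. The protocol counts hospital days from 1 under Reserpine Dosing and study days from 0 under Physiological Monitoring; the two describe the same calendar.

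| Event | Interval added | Cumulative | Study day (from 0) | Hospital day (from 1) | Clock |
|---|---|---|---|---|---|
| Admission | – | 0 h | 0 | 1 | 10 AM |
| Infusion 1 | 24 h | 24 h | 1 | 2 | 10 AM |
| Reserpine or placebo | 60 h | 84 h | 3 | 4 | 10 PM |
| Infusion 2 | 12 h | 96 h | 4 | 5 | 10 AM |
| Release | 48 h | 144 h | 6 | 7 | 10 AM |

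144 / 24 = 6 exactly, so release falls at the admission hour six dates later and the stay has 6 nights whatever that hour is. The stated 5 nights does not reproduce. The 7-day description, the 48 h readings and the day 6 aliquot all fit 6.

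**Payment.** The stated maximum reproduces only with 5 nights and the bonus applied to the whole sum:

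- 5 nights, bonus on everything: 1.10 × (30 + 5 × 150) = 1.10 × 780 = $858, as stated.
- 5 nights, bonus on ward nights only: 30 + 1.10 × 750 = $855, not as stated.
- 6 nights, bonus on everything: 1.10 × (30 + 6 × 150) = 1.10 × 930 = $1,023.

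The difference is 1,023 − 858 = $165 per completer, and 30 × 165 = $4,950 if all 30 complete.

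**Loss if 5 nights were followed.** A 5-night stay from the day 0 admission ends on study day 5. The protocol gives no discharge hour for that case; 10 AM (24 h after infusion 2) to midnight (38 h) is an assumed range. The post-infusion schedule has 15 distinct times: 5, 15, 30 and 60 minutes, then 2, 3, 4, 6, 8, 12, 18, 24, 30, 36 and 48 h, the 1 h entry repeating the 60-minute one. After infusion 2, 30 h is day 5 at 4 PM, 36 h is day 5 at 10 PM and 48 h is day 6 at 10 AM.

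| Day 5 discharge | Readings lost, of 15 | Observation lost, of 48 h | Day 5 Beck score |
|---|---|---|---|
| 10 AM to before 4 PM | 3 (30, 36, 48 h) | 18 to 24 h | lost |
| 4 PM to before 10 PM | 2 (36, 48 h) | 12 to 18 h | kept |
| 10 PM to midnight | 1 (48 h) | 10 to 12 h | kept |

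The second 24 h urine after the combination runs from day 5 at 9:30 AM to day 6 at 9:30 AM. Discharge at 10 AM leaves 0.5 h of it and discharge at midnight 14.5 h, so it is incomplete in every case. The day 6 aliquot is lost in every case. All readings up to 24 h are kept in every case.

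**The case against.** The strongest reply is that this is a clerical slip. The 5-night total summarises an explicit rule in the preceding sentence, and the 7-day description and 48 h readings point the same way. Staff who follow the rule lose nothing; the sixth night is payable at the stated rate; design, doses, randomisation, sample size and analysis do not change. All of that stands, and it limits the weight of the point. It does not make the two figures right, and neither of them is background text.

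The data-loss scenario is also open to challenge. It requires the ward to pass over the 48 h rule, and the discharge hours are assumed. That is fair: the losses are conditional and the error does not depend on them. The table is also not a full count. Section 4.f.1 schedules routine 8 PM measurements on day 5, which any discharge before 8 PM would lose as well.

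The list of routine monitoring days stops at day 5, and days 0 to 5 span five nights, which may be where the figure came from. That cannot justify release on day 5, because the same part of section 4.f.1 schedules 48 h readings and a day 6 aliquot.

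Finally, the day 5 Beck score is the only one on a day after the combination even on the full timetable, since release on day 6 at about 10 AM precedes 4 PM. The 5-night figure does not cause that and correcting it does not cure it. It only explains why losing the day 5 score would matter.

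**Conclusion.** The concern holds. The protocol's intervals fix a stay of 144 h, or 6 nights, against 5 stated, and the $858 maximum is the 5-night total where the timetable gives $1,023. The length of stay rests only on stated intervals; because the 24 h lead time is a minimum, a longer one could only lengthen the stay. The payment figure also assumes that the bonus applies to the screening payment as well as the nights, which is the reading that reproduces $858.

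This is an inconsistency in operations and payment that should be corrected. It does not affect power, alpha, the analysis or the 0 to 24 h comparison of the two challenges. Data are lost only if the 5-night figure overrides the 48 h rule, by an amount that depends on an unstated discharge hour. The consent form and bed booking were not available, so whether they carry the error is unknown.

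**What to change.** In section 4.f.2, replace the 5-night total with 6 nights (144 h, from 24 h before the first infusion to 48 h after the second). In section 4.k, change the maximum payment to $1,023. Check that the consent form and the bed booking agree with both figures.

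The cost is two changed figures and that check. The stated payment maximum rises by $165 per completer, at most $4,950 in all, and up to 30 bed-nights are needed beyond the stated 5 per subject. No dose, randomisation, endpoint or analysis rule changes.

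### The stated stay of 5 nights and the $858 maximum payment contradict the protocol's own intervals, which require 6 nights and $1,023

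*Protocol*

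**What the plan says.** Section 4.f.2 (Time, Study Sessions) admits subjects "24 hours before the first methamphetamine challenge" and keeps them on "the ward until 48 hours after the last methamphetamine challenge dose". Its next sentence gives the total: "The total duration of GCRC admission is 5 nights".

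The spacing of the challenges is in section 4.f.1 (Reserpine Dosing): "All groups receive methamphetamine 15 mg 60 hours before and 12 hours after reserpine". Reserpine or placebo is given at about 10 PM on the fourth hospital day. The same paragraph sets the admission lead time as a minimum of one day, not as exactly 24 hours.

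Other places that bear on the length of stay:

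- Section 4.a opens with "This 7-day double-blind, parallel-group, placebo-controlled inpatient study".
- Section 4.f.1 (Physiological Monitoring) puts the challenges on study days 1 and 4, with readings out to "18, 24, 30 36 and 48 hours after the infusion".
- Section 4.f.1 (Biosample Measures): "On days 1, 4, and 6, aliquots will be sent for qualitative drugs of abuse screens".
- Section 4.f.1 (Urine Samples) collects all urine in 24-hour intervals starting at 9:30 AM, for MHPG-sulfate.

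Section 4.k pays $30 for the second screening session and $150 for each night on the ward, adds a 10% bonus for completing all procedures, and gives $858.00 as the most a subject can earn.

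**The concern.** The night count and the maximum payment are working figures: one is used to book the ward, the other to tell subjects what they can earn. If both rest on 5 nights, they cannot deliver the stay that the sentence just before the night count requires. A subject who completes that stay would also be owed more than the stated maximum.

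There is a possible consequence for the data. If staff went by the night count, subjects would leave on day 5, before the last scheduled measures after the second challenge. The matching measures after the first challenge would all have been taken, since they end before reserpine is given at 60 hours.

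**Working it through.** **Length of stay, from the intervals**

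- Admission to challenge 1: 24 h (4.f.2)
- Challenge 1 to reserpine: 60 h (4.f.1)
- Reserpine to challenge 2: 12 h (4.f.1)
- Challenge 2 to discharge: 48 h (4.f.2)

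24 + 60 + 12 + 48 = 144 h, and 144 / 24 = 6 nights.

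**Check against the clock**

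Reserpine at 10 PM on hospital day 4 gives:

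- Challenge 1, 60 h earlier: 10 AM on hospital day 2
- Admission, 24 h before that: 10 AM on hospital day 1
- Challenge 2, 12 h after reserpine: 10 AM on hospital day 5
- Discharge, 48 h later: 10 AM on hospital day 7

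That is 6 nights over 7 calendar days, as in section 4.a. The monitoring paragraphs number from day 0, so admission is day 0, the challenges are days 1 and 4, and 48 h after the second is day 6. The count is again 6 nights. The two day-numbering schemes differ by one but lead to the same answer.

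**The stated payment, reproduced first**

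- 5 nights, bonus on everything: (30 + 5 × 150) × 1.10 = 780 × 1.10 = $858, an exact match.
- 5 nights, bonus on ward pay only: 30 + 750 × 1.10 = $855, no match.
- 5 nights, no bonus: $780, no match.

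The stated maximum therefore rests on 5 nights with the bonus applied to the full sum. By the same rule, 6 nights give (30 + 6 × 150) × 1.10 = 930 × 1.10 = $1,023. The difference is 1,023 − 858 = $165 per subject.

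**What a 5-night stay would lose**

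Five nights from day 0 end on day 5. The protocol gives no discharge hour for that case, so the hours below are assumptions. After challenge 2, the first urine interval runs from 9:30 AM on day 4 to 9:30 AM on day 5. The second runs to 9:30 AM on day 6.

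| Assumed discharge, day 5 | Hours after challenge 2 | Timed readings lost | Second urine collection obtained |
|---|---|---|---|
| 10 AM | 24 | 30, 36, 48 h | 0.5 of 24 h |
| 4 PM | 30 | 36, 48 h | 6.5 of 24 h |
| 8 PM | 34 | 36, 48 h | 10.5 of 24 h |
| Midnight | 38 | 48 h | 14.5 of 24 h |

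The 8 PM row is the natural one if the day-5 schedule is kept: "Subjective measures will be obtained daily at 8 AM, 4 PM, and 8 PM on study days 0, 2, 3 and 5". In every row the 48 h assessment, the day-6 aliquot and the second complete MHPG collection are lost. In every row the readings through 24 h and the first complete collection survive.

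**The case against.** The strongest reply is that the night count is a slip in a summary sentence. The sentence before it, the 7-day study length, the 48-hour readings and the day-6 aliquot all point to the longer stay, and a site that follows the procedures will keep subjects for 6 nights. Pay is set per night, so the rate corrects itself and only the printed total is wrong. This stands as far as it goes. It makes data loss a risk that depends on which figure the ward follows, but it does not make either stated figure right.

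Two stronger readings are tempting, and the protocol supports neither.

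A reader might infer that the before/after comparison of the methamphetamine response is compromised. Section 3 describes blood pressure peaking at 2 minutes and heart rate at 10 minutes after a 30 mg dose, with a plateau by 15 minutes and a slow return to baseline over that day. The readings at 36 and 48 hours therefore carry little of the acute response. One full MHPG collection after challenge 2 remains in any case, and nothing in the protocol says the comparison needs a second.

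A reader might also infer that follow-up is inadequate, because the mouse interaction study in section 3 reports deaths 2 to 5 days after combined dosing and the visible text describes no contact after discharge. That is a separate design preference. The increase in lethality was not statistically significant, the reserpine dose was 3 mg/kg, and other animal work in the same section found fewer deaths or no increase. A telephone call could record a delayed event but not prevent one. Consent pages, where such contact might be described, were also removed from the text at hand.

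One objection changes the fix. Because section 4.f.1 sets the admission lead time as a minimum, 6 nights is itself a minimum until that wording is aligned with section 4.f.2.

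**Conclusion.** The contradiction is certain. The protocol's intervals give 144 hours, or 6 nights, against 5 stated. The $858 maximum reproduces exactly, and only on 5 nights, so it is $165 below what a completer of the required stay would earn.

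The result assumes admission exactly 24 hours before challenge 1, and the bonus rule that reproduces $858. With the bonus on ward pay only, the 6-night figure would be $1,020, but that rule does not reproduce the stated maximum.

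The loss of late measures after challenge 2 is conditional on the 5-night figure being followed, and is limited to what falls after 24 hours. This is a consistency error in two working figures that should be corrected. It is not evidence that the design or its main comparison fails.

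**What to change.** - Section 4.f.2: change the total stay to 6 nights.
- Section 4.k: change the maximum payment to $1,023.
- Section 4.f.1 (Reserpine Dosing): replace the minimum of one day before the first challenge with exactly 24 hours, as in section 4.f.2, so that 6 nights is exact.
- Carry both corrected figures into any other study document that repeats them.

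Cost relative to the stated figures: $165 and one ward night per subject, or at most 30 × 165 = $4,950 in payments if all 30 subjects complete. No procedure changes, because the schedule of measures already assumes the longer stay.

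A single telephone call after discharge is an optional suggestion for the sponsor and not part of this correction.

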This will be according to standard UCSF policy. The following statement is included in the consent form: "If I am injured as a result of being in this study, treatment will be available. The University of California, depending on a number of factors may cover the costs of such treatment. The University does not normally provide any other form of compensation for injury. For further information regarding this, I can either discuss it with the investigators or, if this is not clarified to my satisfaction, I can call the UCSF Committee on Human Research Office at [contact]."

i. Alternatives

The alternative is not to participate

j. Costs to the Subject

There will be no costs to the subject.

k. Reimbursements of Subjects

Subjects will earn compensation starting with the second screening session. This session involves undergoing a comprehensive physical examination and a stress echocardiogram. This session is expected to require 2 to 3 hours; compensation of \$30.00 will be provided. They will receive \$150.00 for

each night they stay on the research ward plus a 10% bonus if they complete all procedures; the total amount participants can earn is \$858.00.

If a subject does not complete the experimental series, they will be paid their earnings up to that time, but will get no bonus. Subjects who actively abuse illicit drugs while on the GCRC will lose all compensation. Payment will be by University of California check. Subjects must provide their home address and a social security number to receive payments for participating in this study.

I. Confidentiality of Records

Subject confidentiality is always a primary concern. Privacy will not be guaranteed. For hospitalized volunteers, there are many possible confidentiality leaks. Prospective subjects will be told of this clearly. Anyone with strong concerns about being identified as a research subject will be encouraged not to participate. Research forms and files are coded by individual code numbers, kept in secure files or on protected computer disks with any identifying information linking to name only available to research personnel involved in the study. In any UCSF hospital patient records, sufficient medical information must be included to conform with JCAH and UCSF hospital record requirements, but possibly embarrassing information will be mentioned, if at all, in only the most circumspect way.

5. **Qualifications of Investigators**

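### The completion bonus is withheld from every non-completer, including subjects withdrawn for safety on a self-reported symptom, so the payment rule gives a modest reason not to report it.

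*Protocol*

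**What the plan says.** **Payment (Protocol 4.k, Reimbursements of Subjects).** For the second screening visit: "This session is expected to require 2 to 3 hours; compensation of \$30.00 will be provided". The inpatient rate is $150, and its terms run: "each night they stay on the research ward plus a 10% bonus if they complete all procedures; the total amount participants can earn is \$858.00". For those who stop early: "If a subject does not complete the experimental series, they will be paid their earnings up to that time, but will get no bonus". The section does not separate withdrawal by the investigator from withdrawal by choice.

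**Length of stay (Protocol 4.f, Time, Study Sessions).** Admission is a day before the first challenge. The stated total is: "The total duration of GCRC admission is 5 nights".

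**Safety withdrawal (Protocol 4.f, Safety Criteria).** At the first challenge, any listed event ends participation; the rule opens: "If any of the following occur during or within 2 hours of methamphetamine dosing in the first challenge session, the subject will not continue in". Criterion 3 of its five is "Reported chest pain or dyspnea". The same item stands in the preceding list, which governs holding reserpine and ending participation. A subject who exceeds the stopping criteria stays under close observation for at least 24 hours before discharge.

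**Expected effects (Protocol 4.g, Risks/Discomforts).** Dyspnea is named among the most common side effects of intravenous methamphetamine.

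**The concern.** The two rules pull against each other at one point. The symptom criterion works only if the subject speaks up. The payment rule treats a subject who speaks up, and is withdrawn, like one who leaves by choice: the bonus goes.

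The timing gives this some weight. By the Study Design section, the first challenge is the only exposure to methamphetamine alone before it is given 12 hours after reserpine or placebo. The Background section gives possible added toxicity of the combination as a reason for doing the study. A subject who had dyspnea at the first challenge and did not mention it would pass this criterion and go on to the second. Because dyspnea is an expected effect, the situation is foreseeable.

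**Working it through.** **Inputs, all from the protocol**
- Second screening visit: $30 (4.k)
- Ward night: $150 (4.k)
- Bonus: 10%, for completing all procedures (4.k)
- Nights: 5 (4.f, Study Sessions)
- Admission to first challenge: 24 hours, one night (4.f, Study Sessions)
- Observation after a stopping criterion: at least 24 hours, one further night (4.f, Safety Criteria)

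**Step 1. Reproduce the stated maximum.**
(30 + 5 × 150) × 1.10 = 780 × 1.10 = $858. This matches exactly. A bonus on ward nights only would give 30 + 750 × 1.10 = $855, which does not match. The bonus is therefore taken on all earnings: 0.10 × 780 = $78.

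**Step 2. Payment after a stop at the first challenge.**
One night before the challenge plus one of observation: 30 + 2 × 150 = $330, or 330 / 858 = 38.5% of the maximum.

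**Step 3. Split what is forgone.**
- Total: 858 − 330 = $528 (61.5% of $858)
- Nights not stayed: 3 × 150 = $450 (52.4%)
- Completion bonus: $78 (9.1%)
- Check: 450 + 78 = 528

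Only the $78 depends on completion as such. The $450 is pay for time the subject does not spend on the ward.

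**Step 4. Sensitivity to nights stayed.**
If observation ran to a third paid night, the subject would get 30 + 3 × 150 = $480 and forgo $378 (44.1%), of which $300 is nights and $78 is the bonus.

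**Step 5. The later checkpoint.**
Reserpine is due 60 hours after the first challenge, so 24 + 60 = 84 hours after admission, when three nights have been stayed. A subject stopped there has earned $480 and forgoes at most $378. The bonus part is again $78.

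**Step 6. Sensitivity to length of stay.**
The protocol's intervals add to 24 + 60 + 12 + 48 = 144 hours, which is six nights, not the five stated. That is a separate inconsistency to reconcile. With six nights the maximum would be (30 + 6 × 150) × 1.10 = $1,023. A subject paid for two nights would forgo 1,023 − 330 = $693 (67.7%): $600 for four nights and a bonus of $93. The structure of the result is unchanged.

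**The case against.** The other side has a good deal to say.

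- **The rule is coherent.** It pays for time on the ward, takes back nothing already earned, and agrees with the stated five nights. This stands: section 4.k contains no error of arithmetic or logic. The gap is that it does not address safety withdrawal.
- **A reader might infer that reporting a symptom costs most of the payment, up to $678 of $858 (79%).** That figure counts only the night before the challenge (30 + 150 = $180). It leaves out the observation of at least 24 hours that follows when stopping criteria are exceeded, and reported dyspnea is on that list. Even the $528 is mostly pay for nights not stayed. The part tied to completion is $78.
- **A reader might infer that the safety rule as a whole rests on self-report.** It does not. Only the third of five criteria in each list expressly needs a report. Heart rate, blood pressure and respiratory rate are measured, as is arrhythmia at the first challenge. Confusion and agitation can be observed. Vital signs, including oxygen saturation, are taken repeatedly in the first hour, and screening includes stress echocardiography. Silence removes one safeguard among several.
- **A reader might infer that adverse-event reports on the combination are biased downward.** The documents do not show this. One list is confined to the first challenge and the other governs the reserpine dose. No stopping list is set for the second challenge, and the payment rule is the same in all three blinded groups.
- **The mechanism is assumed.** The protocol does not say that subjects are told the stopping criteria. The consent pages, which are not available here, might qualify the payment terms.

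These points reduce the concern but do not remove it. As written, section 4.k still applies the completion penalty to a subject whom the investigator withdraws after a symptom report.

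**Conclusion.** The point holds in a limited form. The no-bonus rule covers investigator withdrawals for safety, and one criterion for such a withdrawal is a self-reported symptom that the protocol expects to be common. The explicit penalty is $78, about 9% of the maximum.

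This rests on five nights, a bonus on all earnings (which reproduces the stated total), one observation night, and no exception elsewhere, such as in the consent form. What is established is an incentive. Neither actual concealment nor bias in the results can be concluded from the documents. It is a cheap improvement, not a flaw that threatens the trial.

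**What to change.** Add one or two sentences to section 4.k: a subject withdrawn by the investigator under the safety criteria of section 4.f is paid for every night stayed, including observation nights, and does not forfeit the completion bonus. Say whether the bonus is then the full $78 or 10% of earnings to date (0.10 × 330 = $33 for a stop at the first challenge). Put the same words in the consent form and tell subjects before the first infusion. Keep the no-bonus rule for voluntary withdrawal. No dose, threshold or stopping criterion changes.

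**Cost.** At most $78 per subject withdrawn for safety. If 5% to 20% of the 30 subjects were withdrawn (an assumption, not a protocol figure), that is 1.5 to 6 subjects and about $117 to $468 in total. There is a slight incentive to over-report, limited because nights not stayed remain unpaid.

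Paying for those nights as well would restore the full $858, but it would also pay $450 for leaving three nights early on an unverifiable symptom. That is optional, and for the sponsor and the ethics committee to weigh.
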